Across the sites 60 patients will be enrolled to achieve 40 FEAST patients who will fully complete this study at the MUSC Institute of Psychiatry, Brain Stimulation Service (BSS) in Charleston, SC, and at GRU in Augusta, GA and Aiken, SC. At both MUSC and GRU, roughly matched 30 patients (each) will also be recruited from those scheduled to receive UB RUL ECT to obtain a cohort of 40 RUL comparison patients. The FEAST and UB RUL ECT groups must meet identical inclusion/exclusion criteria and will undergo identical evaluation procedures. The only difference between the groups will be that one receives FEAST and other UB RUL ECT. The treatment received by the UB RUL ECT group will not be affected by participating in this protocol. This is an open label, non-randomized, non-masked study. Separate consent forms will be used in each group. We are thus asking FDA permission to study 60 patients with FEAST. An additional 60 patients will be studied who receive conventional ECT. Even though they are getting conventional ECT, they are covered by this FDA IDE as their data will be used for comparison purposes with FEAST.

Patients will be selected from those referred for ECT for the treatment of major depressive episode. To verify diagnosis, the SCID-P will be administered to derive DSM-V diagnosis (unipolar or bipolar major depressive episode) and relevant subtypes and specifiers (American Psychiatric Association, 2013).

Inclusion and exclusion criteria are presented in Table 2. Briefly, patients will be between the ages of 18 and 90 years and will provide informed consent. Exclusions include: history of schizophrenia, schizoaffective disorder or any non-mood disorder psychosis, rapid cycling bipolar disorder, central nervous system illness other than conditions associated with psychotropic exposure, alcohol or substance abuse or dependence in the past 3 months, pregnancy, epilepsy, inability to have stable medications, and ECT within the past six months.

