There is no evidence that gender or minority status is related to response to ECT or by extension to FEAST (Nobler and [name], 1996). Patient recruitment will reflect the referral patterns to MUSC and GRU. Given the gender difference in the prevalence of major depressive episode it is expected that approximately two-thirds of the sample will be female. It is expected that the sample composition will be approximately 85% Caucasian, 14% African-American, 1% Hispanic or other ethnic group in line with the historical referral basis for the MUSC ECT service and the GRU ECT services.

B.2 Inclusion Exclusion/Criteria

Table 2 presents the inclusion/exclusion criteria for the next FEAST study. These criteria have been consistent since the original FEAST IDE with the following exceptions. First, all psychiatric diagnoses now are based on DSM-V instead of Research Diagnostic Criteria (RDC) (Spitzer et al., 1978) or DSM-IV. The second change is more substantive. In the previous iterations of this IDE, we required that patients be medication free during the FEAST course, other than lorazepam (up to 3 mg/d). Maintaining this medication-free status was deemed untenable. There is now randomized, blinded, placebo-control evidence from a large multi-center study that the efficacy of traditional ECT is enhanced by the co-administration of antidepressant medication ([name] et al., 2009). Thus, medication-free status presents an ethical dilemma as it may diminish the likelihood of clinical benefit. Second, in clinical practice ECT patients commonly receive concomitant psychotropics. Continuing to require medication-free status in the FEAST group would introduce a fundamental confound in comparison with the UB RUL ECT group. The approach we now take excludes exposure to medications that may interfere with ECT efficacy (anticonvulsants, higher doses of anxiolytics) or present a safety risk (e.g., lithium), while permitting medications that may augment clinical efficacy (antidepressants, atypical antipsychotics). Medication status will be carefully tracked and explicitly compared in the two groups.

Table 2. Inclusion and exclusion criteria for study participation

Inclusion Criteria

Age between 18 and 90 years (inclusive)	
Diagnosis of major depressive episode	SCID to derive DSM-V
Pretreatment HRSD score ≥ 21	Hamilton Rating Scale for Depression (24-item)
ECT indicated	Physician evaluation
Willing and capable of providing informed consent	Physician evaluation

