Exclusion Criteria

History of schizophrenia, schizoaffective disorder, other functional psychosis, or rapid cycling bipolar disorder	SCID to derive DSM-V; rapid cycling defined as \geq four episodes in past year
History of central nervous system illness or insult other than conditions associated with psychotropic exposure (e.g., tardive dyskinesia)	Physician evaluation; medical history
Alcohol or substance abuse or dependence in the past year (DSM-V)	Physician evaluation
Secondary diagnosis of a delirium, dementia, or amnestic disorder (DSM-V), pregnancy, or epilepsy	Physician evaluation
Requires especially rapid antidepressant response due to suicidality, psychosis, inanition, psychosocial obligations, etc.	Physician evaluation
No anticonvulsant mood stabilizers (e.g., Depakote, Tegretol, Lamictal); No lithium; No psychostimulants (e.g., Ritalin, Adderall); Allowed medications during FEAST/ECT: Antidepressants, including bupropion Atypical antipsychotics; Hypnotics for sleep; Anxiolytics (limited to up to 3 mg equivalents/day lorazepam)	Treatment history and physician evaluation

ECT in the past six months	Physician evaluation; medical history
----------------------------	---------------------------------------

Patients with a history of schizophrenia, schizoaffective disorder, or any other (non-mood disorder) psychotic condition, or substance abuse within the past year are excluded. At screening, patients will be administered the Hamilton Rating Scale for Depression (24-item version) (Hamilton, 1967) and must have a score of at least 21. Patients who meet these conditions and the other inclusion/exclusion criteria in Table 2 will be considered for participation. Informed consent will be obtained from all study participants. Capacity to provide consent will be independently documented by a member of the patient's treatment team not involved in the research (likely at MUSC), or have the patient successfully complete a document that shows that they have the capacity to consent to participate (likely at GRU).

The inclusion criteria includes a physician evaluation that ECT is indicated. Medication resistance constitutes but one indication for the use of ECT. The CRF that documents this determination is based on the American Psychiatric Association Task Force Report on ECT (2001) statement of the conditions that justify the primary or secondary use of ECT. The considerations that are weighed in determining whether ECT is indicated include the following:

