Medication Status. Patients will be stabilized on their medications for 7 days and will be withdrawn from lithium and anticonvulsants for at least 5 days. ECT starts after completion of the baseline battery, usually after an additional 1-2 days. PRN lorazepam is limited to 3 mg/d, and is withheld approximately 10 hr before a treatment. A daily log is kept of all medications (psychotropic or otherwise) patients receive. Introduction of any medication during the FEAST (or UB RUL ECT) will be considered a protocol violation but will not lead to termination from the study.

General Treatment Technique. After completion of the pretreatment assessment battery, treatment with FEAST will begin. FEAST will be administered only with the modified Spectrum 5000Q device approved with this IDE application. Treatments are given in the morning, 3 times per week. Pharmacological agents are standardized: atropine (0.4 mg IV), methohexitol (0.75 mg/kg) and succinylcholine (0.75-1.0 mg/kg). [If methohexitol is unavailable, thiopental is substituted (2.0 mg/kg).] Patients are oxygenated by mask (100% O₂) prior to anesthesia and until resumption of

spontaneous respiration. Standardized procedures are used to reduce impedance at FEAST and EEG electrode sites. The impedance of the EEG electrodes is kept ~ 5k ohms.

The "cuff technique" assists in monitoring the duration of ictal motor activity (Fink and Johnson, 1982). The EEG sites are left and right frontal (F7 and F8) and a custom placement for the left and right temporal leads (to avoid overlap with the RUL ECT electrodes). Each EEG site is referenced to the ipsilateral mastoid (Weiner and Krystal, 1993). A detailed manual is available that describes detailed procedures for preparing the FEAST or RUL ECT electrode sites and the EEG sites. As indicated the primary hypothesis tested in this study concerns the ictal EEG collected at every treatment. We predict that seizure onset will be more restricted to the right frontal site with FEAST compared to UB RUL ECT.

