Self-Report ratings. The Inventory of Depressive Symptoms (IDS-SR) (Rush et al., 1985) is completed at baseline, and following completion of the course. This instrument has shown strong psychometric properties and is especially broad in its coverage of depressive symptoms. It has been used in many MDE treatment trials, including STAR*D (Rush et al., 2006).

B.9 Classification of Clinical Outcome and Dropout

Dropout. If, for any reason, there is a lapse of 3 scheduled treatments during a FEAST course (e.g., intercurrent illness, withdrawal of consent), the course is considered terminated. If, for any reason, the patient receives a prohibited psychotropic they are also considered to have dropped out. Patients who withdraw consent for research participation are immediately withdrawn from the research. The Principal Investigator or the Study Physician may withdraw a patient from the protocol at any time if it is deemed in the patient's interest to do so. Examples include emergence of a complicating medical condition, discovery of a previously undiagnosed exclusion criterion, etc.

Response Criteria. Remission is the categorical outcome that has precedence for efficacy determination. However, response status denotes that substantial, but incomplete, benefit has obtained. The a priori criteria for response are consistent across virtually all MDE clinical trials. Based on an assessment 1-2 days following ECT, patients are responders if they have a $\geq 50\%$ reduction in HRSD₂₄ scores relative to preECT baseline. All other patients are nonresponders.

Remission Criteria. Especially when ECT is the treatment modality, the goal is remission and not response (Thase, 2003, Paykel, 2002, McCall, 2014, McCall, 2013). Remitters in this study must satisfy final response criteria and have a 1-wk postECT HRSD ≤ 10 . The remitter criteria are stringent, given the use of the 24-item HRSD and the severity of illness at study entry.

B.10 Assessment of Function and Attitudes Toward Treatment

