Thus, this protocol attempts to minimize the risks of adverse cognitive effects by both attending to the patient and treatment factors that impact on cognitive outcomes. The fact that participants in this protocol will be under close observation and supervision provides another set of safeguards, allowing for rapid and sensitive detection of adverse effects and early intervention.

Psychiatric Adverse Effects. The major psychiatric adverse effects, as discussed at length in Section III.C, are the emergence of postictal delirium or agitation and a switch to hypomania or mania. As noted, it cannot be predicted which patients will manifest postictal delirium, and this state may be seen at any treatment in the course. It may occur only once or twice or it may be manifest at all treatment sessions. Depending on the severity and persistence of the agitation, various interventions will be considered. First, the patient should be made safe such that thrashing movements or attempts to leave the stretcher can be restrained without harm. Second, the IV line needs to be secured so that IV access is not lost if the agitation becomes more profound. Third, the amount of environmental stimulation should be limited, and the patient monitored in a quiet, dimly light area. Fourth, if pharmacological intervention is needed, the preferred agent is IV midazolam, although other benzodiazepines and the anesthetic agent may be used.

The induction of hypomania or mania is a relatively rare complication, almost invariably seen in patients known to have bipolar illness. There is no consensus in the field about how to manage such patients. We take a conservative approach and suspend ECT when emergent hypomania or mania is seen. Commonly, within a few days, these symptoms subside spontaneously and the depressive disorder is manifest. If the interruption is less than 3 scheduled treatments, such patients can return to the research protocol. On the other hand, if the symptoms are sufficiently prominent and concerning that immediate institution of a mood stabilizer is

warranted, these patients will be dropped from the protocol and treated on an open clinical basis.

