The experience of being awake while still paralyzed is frightening and is especially likely to occur with treatments that result in rapid return of orientation following seizure termination. We have seen some instances of this phenomenon with Magnetic Seizure Therapy that were managed by administering an additional (half) dose of the anesthetic after seizure termination. The possibility of such a phenomenon will be closely monitored in the FEAST patients as it is expected that they have especially rapid return of orientation. In such circumstances, we will determine whether increasing the anesthetic dose prior to the electrical stimulation or giving a second post-seizure dose is the most effective strategy.

C.4 Other Risks of the Research

Three aspects of the research may involve other risks. These are the medication restrictions prior to and during the FEAST trial, the potential delay in the start of pharmacotherapy or continuation ECT following the end of the FEAST trial, and the confidentiality of the data.

Medication Washout. There is a 5-day medication washout of lithium or other anticonvulsants or stimulants prior to the start of the research evaluation procedures. All other psychotropic medications are held stable other than PRN use of lorazepam (up to 3 mg/d). The holding steady of psychotropic medications and the stopping of some medications (anticonvulsants, lithium, stimulants, excessive anxiolytic) may lead to an increase in depressive and related symptomatology, either as a withdrawal reaction or as a worsening of the psychiatric condition. Stopping lithium and anticonvulsants is standard practice for ECT, however. We limit the risks of the medication washout in the following manner. First patients who it is believed cannot tolerate medication withdrawal are excluded from the study (see Table 2). Second, any patient who finds the medication withdrawal intolerable will be withdrawn. Third, any patient who on clinical grounds requires mood stabilizers or changes in medications during the trial are withdrawn and offered the requisite treatment. Patients are in close contact with the MUSC and GRU clinicians and their primary psychiatrists. We have used these procedures in several hundred patients in our ECT clinical services and in previous ECT research at MUSC and GRU and rarely have patients had to be withdrawn from the study due to intolerance of the washout or related factors.

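### For a permitted drug that becomes clinically necessary during the course, one section keeps the patient in the study and another withdraws the patient, and assessment after a medication exit is left unstated

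*Combined protocol and SAP*

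**What the plan says.** Four places govern medication started during the course.

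- IV.B.6, Medication Status: introducing any medication, in either group, "will be considered a protocol violation but will not lead to termination from the study".
- IV.C.4, Medication Washout: "any patient who on clinical grounds requires mood stabilizers or changes in medications during the trial are withdrawn" and offered the treatment they need. The same paragraph reports that, in past use of these procedures, "rarely have patients had to be withdrawn from the study due to intolerance of the washout or related factors".
- IV.B.9, Dropout: if "the patient receives a prohibited psychotropic they are also considered to have dropped out".
- IV.C.3, Psychiatric Adverse Effects: where emergent hypomania or mania calls for immediate start of a mood stabilizer, "these patients will be dropped from the protocol and treated on an open clinical basis".

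Table 2 (IV.B.2) lists what may be taken: "Allowed medications during FEAST/ECT: Antidepressants, including bupropion Atypical antipsychotics", with hypnotics and limited anxiolytics. IV.B.2 also promises: "Medication status will be carefully tracked and explicitly compared in the two groups".

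Post-course measures are timed from the end of treatment: clinician ratings 1 to 2 days after ECT ends (IV.B.8), MRI 24 to 96 hours after the last session (IV.B.5a), and the attitude interview and cognitive tests in the following week (IV.B.10, IV.B.12). IV.B.15 places the primary efficacy analyses in the intent-to-treat sample, which Hypothesis 4 equates with all available HRSD24 data.

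**The concern.** Two instructions give opposite outcomes for the same patient. If a permitted antidepressant or atypical antipsychotic becomes necessary and is started, IV.B.6 keeps the patient and IV.C.4 removes the patient. Two sites with separate clinical teams could each follow the text in good faith and act differently.

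The statistical stake is the post-course visit. CUAMI-SF (Hypothesis 5) and subjective memory (Hypothesis 6) are analysed by covariance models on scores taken after the course, and Hypothesis 3 needs a second scan. A patient withdrawn without that visit contributes nothing to those comparisons. The loss would follow a clinical event, in an open-label, non-randomized comparison where there is little else to protect comparability. Withdrawal would also cut short the medication record that IV.B.2 says will be compared between groups, whereas keeping the patient preserves it.

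**Working it through.** This is a check of the text, and the only arithmetic concerns the enrolment surplus.

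**Which rule applies to which drug**

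| Event during the course | IV.B.6 | IV.C.4 | More specific rule | Settled? |
|---|---|---|---|---|
| Prohibited psychotropic received | stays | withdrawn if clinically required | IV.B.9: dropout | Yes, if the specific rule prevails |
| Mood stabilizer needed for mania | stays | withdrawn | IV.C.3: dropped from protocol | Yes, if the specific rule prevails |
| Permitted drug clinically needed and started | stays | withdrawn | none | No |

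The conflict is the third row. IV.B.9 reaches only prohibited psychotropics and IV.C.3 only mood stabilizers. One might separate the two general rules by saying that IV.B.6 concerns drugs given and IV.C.4 concerns drugs needed. A drug that is needed and then given meets both descriptions, and no order of precedence is stated.

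**Whether assessments follow a medication exit**

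The timings in IV.B.5a, IV.B.8, IV.B.10 and IV.B.12 run from the end of treatment and do not require a completed course. They can therefore be read to apply after an exit. None says that it applies to a patient who is withdrawn, counted as a dropout or dropped from the protocol. IV.C.4 (Delay in Start of Alternative or Continuation Therapy) applies the post-course interval whatever the clinical outcome, but assumes that the patient remains on the stabilized regimen, which a medication exit contradicts. The intent-to-treat wording uses the HRSD24 data that exist and creates no duty to collect more.

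**Which analyses depend on the post-course visit**

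- Hypothesis 1 (threshold at the first treatment): no.
- Hypothesis 2 (ictal EEG at each treatment): no, except 2f, which uses percent change in HRSD24.
- Hypothesis 3 (pre-post fMRI): yes.
- Hypothesis 4: the primary random regression uses weekly HRSD24 and keeps scores before exit; final HRSD24 and remission depend on the visit.
- Hypothesis 5: orientation time is averaged over treatments given, so no; CUAMI-SF, yes.
- Hypothesis 6 (subjective memory): yes. Its covariates also include percent change in HRSD24 and in CUAMI-SF.

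**Enrolment surplus (IV.B.1)**

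- FEAST: "60 patients will be enrolled to achieve 40 FEAST patients who will fully complete this study". Surplus 60 − 40 = 20; 20/60 = 33%.
- UB RUL: 2 sites × 30 = 60 recruited for a comparison cohort of 40. The arithmetic gives the same 33%, but completion is not mentioned, and the surplus could equally serve the matching. An attrition allowance in this group is an inference.

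Either surplus protects numbers. It does not address loss that follows a clinical event.

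**Size of the bias**

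This would need the proportion leaving for a medication reason in each group and the outcome difference between leavers and stayers. The documents give neither, so no figure is offered.

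**The case against.** The strongest reply is that the IV.C.4 sentence is the third item in a list of ways to limit washout risk. In that setting, a change in medications may mean only that a patient could not tolerate the washout or the stable regimen, with IV.B.6 as the operating rule. IV.B.1 also excludes patients who cannot keep stable medications, and IV.C.4 calls related withdrawals rare. This stands in part: the conflict is narrow and probably seldom met. It does not remove it, because the sentence says during the trial and the paragraph speaks of withdrawal from the study.

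A second reply is that IV.B.9 distinguishes dropping out from withdrawing consent, and only the latter is described as immediate withdrawal from the research. Dropout may therefore mean leaving the treatment course with assessments still due. That is a fair reading, and the fix would make it explicit. IV.B.9 also classes everyone who does not meet the response criterion as a nonresponder, which might supply a categorical outcome for an unassessed patient; CUAMI-SF, subjective memory and fMRI have no such default.

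A third reply is that the primary aim is ictal EEG, with efficacy and side effects secondary (IV.B.5, IV.B.13). That stands and limits the weight of the point.

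A reader might go further and infer that post-course data will be lost, that the efficacy result will be biased, or that the intent-to-treat analysis fails. The documents do not support this. They leave the collection of those data unstated, and the Hypothesis 4 regression retains weekly scores up to exit.

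**Conclusion.** The two rules cannot both be followed for a permitted drug that becomes clinically necessary, and the public text does not say which prevails. It also does not say whether post-course assessments continue after a medication exit. The consequence is confined to CUAMI-SF, subjective memory, final HRSD24 and remission, Hypothesis 2f and the second fMRI, in what is probably a small number of patients. The bias cannot be sized in magnitude or direction. The change should be made because the missing data could not be recovered later and the remedy is cheap; the primary EEG aim is not at risk.

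This rests on two assumptions: that IV.B.9 and IV.C.3 prevail over IV.B.6 for the drugs they name, and that the pages missing from the public text, including the consent forms, contain no rule that settles the matter.

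**What to change.** 1. Align IV.C.4 with IV.B.6: in both groups, adding a permitted drug is a logged protocol violation and the patient stays in the study.
2. State in IV.B.9 and IV.C.3 that a prohibited psychotropic or a required mood stabilizer ends study treatment but not assessment.
3. For every treated patient who has not withdrawn consent, obtain the end-of-acute assessments already in Table 5, and the MRI if the patient agreed to it. Use the existing windows after the last study treatment, before alternative treatment where clinically possible.
4. Flag any score taken after other treatment has begun, and add a sentence to IV.B.15 that Hypotheses 4 to 6 will be reported with and without flagged scores.

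The cost is wording in a few paragraphs, one analysis sentence and a few extra visits with instruments already in use. The downside is that some scores will be contaminated by later treatment, which is why they are flagged and reported both ways.

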With respect to optimization of treatment, the key issues are the choice of sites for electrode positioning and the dosing strategy. In using the 1.25" diameter anterior electrode (as opposed to a smaller anode), the degree of focality is reduced and this should protect efficacy. We do not have sufficient knowledge of the functional neuroanatomy to justify greater focality (Nobler et al., 1994, Nobler et al., 2001, Seminowicz et al., 2004). Rather, at this stage, the more limited goals are to restrict seizure onset and expression largely to regions in the right prefrontal cortex (PFC), with virtually no stimulation in left PFC or left or right medial temporal lobe (MTL). In positioning the anode in the area of the Fp2 site in the 10/20 International EEG System, current density will peak broadly through the right anterior PFC. Furthermore, we have taken two steps to ensure that FEAST is not under-dosed. EEG seizures without convulsion are very rare with conventional ECT (Boylan et al., 2001), but may be more frequent with FEAST. Research groups differ in whether or not motor manifestations are required in defining the seizure threshold (ST). In this protocol, we will note the intensity level that results in an "EEG only" seizure, but require that EEG seizure manifestations be clear-cut and last at least 15 s to define the ST value used for subsequent dosing. Second, at any point after the fifth treatment, a clinical evaluation team can recommend a dosage increment, up to 9 x ST. Thus, in this first examination of FEAST, to protect efficacy we have deliberately erred on the side of sacrificing the degree of focality, while also allowing some flexibility in dosing. With stimulation at these levels, it is very unlikely that FEAST will be markedly ineffective, unlike low dosage RUL ECT ([name] et al., 1987b, [name] et al., 1993). Rather, to determine whether there is any effect on efficacy, a substantial number of patients will have to be treated in a masked, randomized protocol (which is planned following this study). Our published data (Nahas et al., 2013a) has demonstrated that FEAST has marked antidepressant effects. However, in the absence of a masked, randomized comparison with traditional ECT, equivalence in efficacy is unknown. This study focuses on the mechanistic issue and attempts to demonstrate that seizures induced by FEAST show robust electroencephalographic activity in frontal electrodes, but reduced activity in

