The criterion for an adequate seizure is ≥ 20 s EEG duration. Subconvulsive stimuli, which occur only during titration sessions, are followed 20 s later by restimulation. Up to 5 stimulations are permitted at titration. Using these criteria, across our two of our recent studies, only 3 out of 1,372 treatment sessions were terminated without an adequate seizure (all due to very high thresholds at the first treatment). Additional monitoring includes continuous display of three channels of ECG (leads I, II, IV), heart rate, blood pressure, and pulse oximetry. At each treatment, the 4 EEG channels are digitized and along with treatment parameters automatically entered into a database using the MECTA EMR (electronic Medical Record) software. The intervals to return of spontaneous respiration and eyes opening upon command are also recorded.

FEAST Stimulus Dosing. After completion of the pretreatment assessment battery, treatment with FEAST will begin. FEAST will be administered using a modified spECTrum 5000Q device. In this study, stimulation parameters at titration will be restricted to an ultrabrief electrical stimulus (0.3 ms pulse width) and unidirectional administration. The amplitude of the constant current during each pulse will also be fixed at 800 mA. Train duration (1.5-8 s) and pulse frequency (30-80 Hz) will be the primary parameters manipulated to adjust dosage relative to seizure threshold (see Table 4). [One suprathreshold setting involves increasing pulse width to 0.5 ms].

At the first treatment, the empirical titration procedure is used to estimate ST ([name] et al., 1987c, [name] et al., 1987d, [name] et al., 1991). This procedure at the first session ensures that the lowest charge needed to evoke a seizure is

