Only 6 parameter combinations will be used at initial titration, with a range of charge from 9.6 to 307.2 mC. If a patient does not have an adequate seizure at the highest of these settings (307.2mC) they will exit the protocol and be offered conventional ECT. [This has not occurred in any of the patients who have received FEAST.] The highest dosage that can be used in this study is 576 mC, the same as the maximal output of a standard domestic Spectrum 5000Q (576 mC).

The stimulating electrodes consist of a small (1.25") round stainless steel electrode and a larger poster stainless steel electrode (2 x 3") that attaches in a standard manner to the MECTA remote-treat or standard stimulus cables. This smaller electrode will be placed anteriorly with the lower boundary just above the center of the right eyebrow. The larger posterior electrode is concave in shape to better couple to the scalp. The posterior electrode will be placed tangential to the midline and extend across the right supplementary motor cortex. The medial position of this electrode will be adjacent to the line connecting the nasion and inion and with the posterior boundary 1.0" anterior to the vertex, with the lateral portion extending over the right hemisphere. A self-adhesive locator will be used to position the anterior anode electrode, ensuring restriction of any conductant gel to the geometry of the anode.

Unless otherwise contraindicated, all patients will be premedicated with atropine (0.4 mg IV) to block the parasympathetic effects of electrical stimulation (approximately 2 minutes prior to anesthetic induction). As indicated, methohexitol (1.0 mg/kg) will be used as the general anesthetic and succinylcholine (0.75 mg/kg) will serve as the muscle relaxant. Dosing of these agents after the first treatment will be based on anesthetic response. Patients will be oxygenated from prior to the induction of anesthesia until the return of spontaneous respiration.

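### The limit of five titration stimulations cannot reach the 307.2 mC exit test, Table 4 has no dose for a threshold of 307.2 mC, and two EEG durations (15 s and 20 s) define threshold

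*Combined protocol and SAP*

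**What the plan says.** Section IV.B.6 (FEAST Procedures), under General Treatment Technique, sets the limit: "Up to 5 stimulations are permitted at titration". The same paragraph requires for an adequate seizure at least "20 s EEG duration. Subconvulsive stimuli, which occur only during titration sessions, are followed 20 s later by restimulation".

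Under FEAST Stimulus Dosing, the same section gives Table 4 and says: "Only 6 parameter combinations will be used at initial titration, with a range of charge from 9.6 to 307.2 mC". The exit rule follows: "If a patient does not have an adequate seizure at the highest of these settings (307.2mC) they will exit the protocol". A bracketed remark adds: "This has not occurred in any of the patients who have received FEAST". The section sets a minimum treatment dose of about six times ST, refers to Table 4 for it, and puts the maximum charge at 576 mC. It says that ST is judged on EEG but gives no duration at that point.

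Section III.D.2 (FEAST Electrodes), describing this protocol, says that the investigators will "require that EEG seizure manifestations be clear-cut and last at least 15 s to define the ST value used for subsequent dosing".

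First-session ST is the outcome for Hypothesis 1 (Section IV.B.15), on the log10 scale. That section and Section IV.D.5 say that both groups follow the same titration schedule.

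**The concern.** Two instructions in the same procedures section cannot both be followed. An operator who obeys the limit stops after 153.6 mC with a patient who has not seized. The only stated exit condition, failure at 307.2 mC, has not been tested. An operator who goes on to 307.2 mC breaks the limit. If that stimulus works, the operator has an ST for which Table 4 prescribes no dose.

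The two EEG durations raise a related problem. A seizure of 15 to 19 s meets the ST definition in Section III.D.2 but is not adequate under Section IV.B.6. No text says whether the patient is then restimulated.

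First-session ST sets every later FEAST dose and is the Hypothesis 1 outcome in both arms. Two sites could settle these points differently and so record different values for similar patients.

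**Working it through.** **Reproducing Table 4.** Section III.D.6 gives charge = 2 × current × pulse width × frequency × duration. For the first titration step, 2 × 0.8 A × 0.3 ms × 20 Hz × 1 s = 9.6 mC. The formula reproduces all 15 charges in Table 4.

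**Five against six.** Each step doubles the one before, so step k is 9.6 × 2^(k−1):

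| Stimulation | Charge (mC) |
|---|---|
| 1 | 9.6 |
| 2 | 19.2 |
| 3 | 38.4 |
| 4 | 76.8 |
| 5 | 153.6 |
| 6 | 307.2 |

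No text allows a higher start or a skipped step. The exit test at 307.2 mC therefore needs six stimulations.

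**Which thresholds have a dose.** Dividing each dosing charge by its stated multiple gives the ST that the row serves:

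- 6×ST block: 57.6/6 = 9.6; 115.2/6 = 19.2; 230.4/6 = 38.4; 460.8/6 = 76.8; 576/3.75 = 153.6.
- 9×ST block: 86.4/9 = 9.6; 172.8/9 = 19.2; 345.6/9 = 38.4; 576/7.5 = 76.8.

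Neither block has a row for ST 307.2 mC. Six times that value is 1,843.2 mC. The most that can be given is 576/307.2 = 1.875 times ST. The 6×ST block covers exactly the five thresholds that five stimulations can identify, so the dosing rows fit the limit of five and the titration rows fit six.

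**15 s against 20 s.** Take a 17 s seizure at 19.2 mC. Under the 15 s definition, ST is 19.2 mC and the 6×ST dose is 115.2 mC. If 20 s governs, the patient is restimulated at 38.4 mC. An adequate seizure there makes ST 38.4 mC and the dose 230.4 mC. Recorded ST moves by a factor of 2 (0.301 on the log10 scale). The effect on the assigned dose of moving up one step is:

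- 6×ST block: 115.2/57.6 = 2; 230.4/115.2 = 2; 460.8/230.4 = 2; 576/460.8 = 1.25.
- 9×ST block: 172.8/86.4 = 2; 345.6/172.8 = 2; 576/345.6 = 1.67.

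**Parameter wording.** Section IV.B.6 says "Train duration (1.5-8 s) and pulse frequency (30-80 Hz) will be the primary parameters manipulated to adjust dosage relative to seizure threshold", and of pulse width, "One suprathreshold setting involves increasing pulse width to 0.5 ms". Nine of the 15 Table 4 rows fall outside those frequency or duration ranges: the five rows at 20 Hz (one of which also has a 1 s train) and the four at 90 Hz. Table 4 also uses 0.4 ms once.

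**Reach.** Section III.D.6 reports that all published pilot patients seized by 43.2 mC. That lies between steps 3 and 4 here. If total charge carries over from the pilot schedule, those patients would have seized by the fourth stimulation.

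**The case against.** The limit of five looks like a carry-over: the pilot titration in Section III.D.6 had five settings, and the six-setting text with its exit rule is the more specific. Hardly any FEAST patient should get that far. Section IV.B.9 also lets the investigator withdraw a patient at any time in the patient's interest. The likely origin and the small reach both stand. The general withdrawal power does not settle which titration rule applies, or what dose goes with ST 307.2 mC.

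On seizure duration, 15 s can be read as the definition of ST and 20 s as a separate test of adequacy. The 15 s wording sits in the rationale, while the procedures section gives 20 s. That makes this part mainly a text correction. It does not remove the ambiguity, because Section III.D.2 speaks of this protocol and ties the 15 s to later dosing.

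Several stronger inferences are tempting and not supported:

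- **Hidden under-dosing at ST 153.6 mC.** Table 4 shows the 3.75 multiple, and the minimum-dose sentence points to Table 4.
- **An estimated number of affected patients.** Section IV.B.6 cites 3 of 1,372 sessions without an adequate seizure, but does not give the modality or pulse width of those studies. The pilot EEG duration of 57 ± 47 s comes from a pilot with a motor-based adequacy criterion and is not limited to titration. Neither gives a rate for this schedule.
- **Material damage to Hypothesis 1.** The documents give no distribution of ST in either arm, so no bias can be calculated.
- **Mis-dosing from the parameter ranges.** That wording defers to Table 4, whose settings are exact.

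**Conclusion.** The point holds as a minor contradiction in operative text. As written, titration cannot be followed for a patient who does not seize at 153.6 mC, and no dose is given for ST 307.2 mC, where the maximum is 1.875 times ST. The second inconsistency, 15 s against 20 s, could move recorded ST by one doubling for a seizure of 15 to 19 s, and the assigned dose by a factor of 1.25 to 2.

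The first case should be very rare in the FEAST arm. That judgement rests on the pilot result and on total charge being comparable across schedules. The documents give no frequency for the second case. Hypothesis 1 expects higher thresholds with conventional treatment, so a ceiling would, if anything, be met more often in that arm. This is a reason to use one ceiling in both arms, not evidence of bias. The primary ictal EEG aim is not directly affected.

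**What to change.** Make the stimulation limit and the exit rule agree, in one of two ways:

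1. Change the limit in Section IV.B.6 to six stimulations, and state that FEAST patients with ST 307.2 mC exit to conventional ECT because six times ST cannot be delivered. Such a patient still has a measured ST for Hypothesis 1. The cost is one extra stimulation for a very rare patient.
2. Keep five stimulations, delete the 307.2 mC step from Table 4 and the text, and exit after failure at 153.6 mC. This matches the existing dosing rows. The cost is an earlier exit for that rare patient, with no measured ST.

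Whichever is chosen, apply the same titration ceiling in both arms.

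State in Section IV.B.6 that 20 s of EEG seizure is the single criterion for ST and for restimulation in both arms, and correct Section III.D.2 to match. A patient with a 15 to 19 s seizure then receives a further stimulation in that session.

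As an editorial matter only, align the duration, frequency and pulse-width wording with Table 4 (1 to 8 s, 20 to 90 Hz, 0.3 to 0.5 ms).

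All of this takes a few lines. It needs no extra patients and no change to the planned analysis.
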